Clinic Recruitment:

Newly referred patients to the interdisciplinary clinics will be pre-screened for eligibility prior to their first clinic visit by a study team member. The patients who meet eligibility criteria will be contacted via phone by a study team member. During the call, we will briefly introduce the study aims, intervention, and different groups. We will request the youth and family to consider participation and will thoroughly discuss the study at the consent

(baseline) visit. The study team member will obtain the eligible participants' email address and send them a recruitment flyer via email if interest is expressed.

AltaMed referral/recruitment:

Patients that meet age and/or BMI criteria, will be provided with study recruitment material and/or the patient will be referred to the study team by AltaMed providers/staff. The study team will acquire patients name, age, BMI (if available) and contact information.

Initial Visit (all participants):

1. Study team member will meet in person/virtually with eligible participants and provide details about the study procedures, obtain written/electronic permission from one parent/legal guardian and assent from minor participants or consent from participants 18 years of age and answer any questions the participants and their parent/legal guardian may have.
- a. Upon obtaining consent from one parent or guardian and assent from each youth to participate in the study, participants will be randomized to one of 3 intervention arms (**AppCoach vs. App vs. Clinic**). If participant is consented via mail, the randomization will occur during the second part of visit 1. The participant will have the option of curbside pickup or mailing of study supplies. If consenting via mail, the study team will mail supplies to participant after receiving signed consent back. If consenting electronically via REDCap or DocuSign, study team will mail study supplies day of consent if possible.
2. All consenting participants will complete a battery of surveys (Refer to Measurements section).
 - a. Youth:
 - i. Yale Food Addiction Scale¹⁹
 - ii. The Center for Epidemiologic Studies Depression scale²⁰
 - iii. The Perceived Stress Scale²¹
 - iv. Behavior Rating Inventory of Executive function²²
 - v. Binge Eating Disorder Screener²¹
 - vi. Physical Activity Questionnaire
 - vii. Satisfaction Survey
 - viii. Food Craving Questionnaire
 - ix. The Adolescent Self-Regulatory Inventory (ASRI)²³

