Up to 404 adolescents (plus 1 parent/youth enrolled) will be recruited for the intervention arms and randomized 1:1:1 via stratified block randomization into one of the following groups: AppCoach, App or Clinic. Demographic information will be collected from all participants. During the intervention period the participants will not attend an inter-disciplinary in-clinic weight management intervention or any other medically supervised weight loss programs. If the participants have underlying comorbidities, they will continue to follow with routine subspecialty providers for standard of care of each underlying condition. Each participant's primary care provider, regardless of the method in which they were recruited (including those recruited from the greater LA county) upon request from participant, will receive a letter from the PI explaining that the individual will be participating in the research intervention during the allotted study period. Parental involvement is not required for those participants randomized to the AppCoach or App group; these participants will complete the intervention independently with the assistance of the coach (if applicable). Parental involvement is required for those participants randomized into the In-Clinic group. Upon completion of the intervention, if the participant was initially referred to a weight management clinic by their primary care provider, they will be offered continued enrollment in the inter-disciplinary weight management clinic for which they were initially referred. In order to further remove barriers to participation, all families who do not have a car will be offered free ridesharing transportation (UBER or Lyft) to- and from CHLA. Additionally, parking validation will be offered for families to park onsite at CHLA for research and/or intervention visits. To increase retention, participants are contacted once per month to maintain engagement. Research staff will provide families with dates of their scheduled assessments/visits. Participants are also given reminder phone calls the day before their assessment/visit.

Trial sites:

A participating trial site must fulfill the following eligibility criteria:

- 1) Have an independent weight management clinic that cares for adolescents.
- 2) The principal investigator and all the clinical research coordinators/staff at the site have been trained on, and understand, the study protocol.

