The Clinic Intervention will utilize the Kids N Fitness Curriculum and will address the following topics over the 6-month intervention:

Session 1: Nutrition and Food Groups

Session 2: Portion Power

Session 3: Real Foods, Fat and Fiber

Session 4: Sugar Savvy

Sessions 5: Healthy Shopping, Healthy Eating

Sessions 6: Special Occasions and Moving Forward

Those youth randomized to the in-clinic control arm will complete the intervention at CHLA or virtually via WebEx. The participant and their parent/guardian will meet with each team member for 20-30 minutes to discuss the topic of the session. The youth will participate in some mild physical activity exercises, such as stretching. Treatment fidelity strategies will be utilized for all three intervention arms to ensure the accurate and precise delivery of each arm as intended. (See Treatment Fidelity Below).

Example Follow up Phone Calls Curriculum Outline (AppCoach):

Call	
1	Introduction: --Coach introduction --Curriculum introduction --Problem Food Identification --Goal setting
2	Personal Motivation: Identify personal motivation and goals of each participant. Have participant identify in and out of home barriers to weight management success. Problem Food Withdrawal Instruct to complete personal story
3	Problem Food Withdrawal -Assess barriers to compliance

4	Problem Food Withdrawal Progress
5	Introduce Snacking Elimination. Identify period of time to start withdrawal Problem Food and Snacking Withdrawal
6	Problem Food and Snacking Withdrawal
7	Problem Food and Snacking Withdrawal
8	Problem Food and Snacking Withdrawal
9	Continue PF and Snacking Withdrawal start food amount reduction Evaluate current barriers to weight management success. Have participant identify one goal to achieve over the next 4 weeks
	Introduce food weigh AppCoach and App: Distribute App setup instructional video
10	Progress report on above. Review frequency of eating out. Review missed weighed meals
11	Review progress, compensation and points earned. Identify successes and barriers. Make goals for second half of intervention
12	Review Face to Face / WebEx Visit 2 Goal of withdrawing from all 10 PF by week 12
13	Review maintenance PF avoidance. Encourage to consider assigning additional PF as tolerated
14	Goal of eliminating snacking by week 14
15	Review maintenance of PF and snacking avoidance

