Statistical analysis: All statistical analyses were conducted in accordance with the planned study protocol.¹⁹ We estimated that 180 participants (60 in each group) would provide 89% power ($\alpha = 0.05$, 2 sided), to detect an effect size of 0.29 which corresponds to a difference of 4.0% %BMIp95 between the three groups. Analyses followed principles of intention-to-treat (ITT) and were performed in nQuery + nTerim 4.0 and Stata/SE 17 (StataCorp, College Station, TX). A two-sided significance level of 0.05 was utilized throughout the analyses. Our analysis approach is based under the assumption that data are missing at random, therefore, imputation using last observation was carried forward, and multiple imputation based on logistic regression model (for BEDS-7 scores only) were utilized to account for missing data. Results from the ITT analysis using imputation were compared as per protocol analysis with completed data. For all outcomes a per-protocol analysis was conducted for: full-program (completed full 24-week intervention period), pre-COVID (completed 24-week intervention prior to 3/15/2020), and during COVID (completed 24-week intervention after 3/16/2020). In addition, to account for impacts of the intervention dosage received on each primary outcome measure we conducted an analysis of participants who were adherent to at least 80% of the prescribed intervention modalities versus those who were nonadherence. Participants' demographic characteristics and baseline anthropometric measurements were reported as appropriately, mean and standard deviation or median and interquartile range for continuous variables, and frequency and percentages for categorical variables. The change in %BMIp95 between week 24 and baseline was assessed using analysis of variance (ANOVA) for all participants via ITT, per-protocol, PreCOVID and during COVID. First, the %BMIp95 was analysed in log scale mixed-effects linear regression model to assess the association between change in %BMIp95 and demographic characteristics (sex, ethnicity,

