Blocked randomization will be utilized, to ensure the groups are balanced in terms of number of subjects and the distribution of potential confounding variables. Blocked randomization will be used to ensure the number of eligible subjects assigned to each group is equally distributed. Block size will be blinded from the primary investigator performing the study.

Potential Risks/Adverse Events and Procedures Used to Minimize the Risks

For purposes of monitoring and reporting adverse events, the following definitions will be used:

Adverse event (AE): any untoward medical occurrence that may present itself during treatment or administration of an intervention, and which may or may not have a causal relationship with the treatment. Adverse events could arise from the study (e.g., breach of confidentiality) or could arise because of the population under study (e.g., a mother reports extensive use of drugs).

Serious adverse event (SAE): Any medical occurrence that results in death; is life-threatening; requires inpatient hospitalization or prolongation of existing hospitalizations; creates persistent or significant disability/incapacity, or a congenital anomaly/birth defect. Such an event could include suicidal ideation or attempted drug overdose or withdrawal, etc.

Adverse events monitoring: Each participant will be evaluated for any adverse events. All events will be graded by their attribution (unrelated to protocol; or possibly, probably, or definitely related to protocol). Any event reported to the Principal Investigator or to designated research associates by the participants or their parents. Events will be carefully documented in a report submitted to the IRBs. The report will include a description of the event; when and how it was reported; any official charts, records, or documentation to corroborate the event or the reporting of the event; and an action plan to prevent future occurrences. All adverse events will be graded as mild, moderate, or severe. Any severe and/or unanticipated adverse event will be immediately reported to the IRBs (within 48 hours of occurrence or recognition). All adverse events will be summarized annually and submitted to the IRBs. Any action resulting in a temporary or permanent suspension of this study (e.g., IRB actions) will be reported to the funding source.

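### The week-24 comparison of arms has no term for site or stratum, and the protocol does not say consistently how randomisation was stratified or by what

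*Combined protocol and SAP*

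**What the plan says.** Enrollment and Retention states that youths are "randomized 1:1:1 via stratified block randomization into one of the following groups: AppCoach, App or Clinic". No stratification factor follows. The only factors called strata anywhere are socioeconomic status, race and ethnicity, under Sampling strategy, and they serve to select neighbourhoods, not to allocate participants.

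Randomization and Blinding refers to blocking twice and to strata not at all. It gives blocking two purposes: "Blocked randomization will be utilized, to ensure the groups are balanced in terms of number of subjects and the distribution of potential confounding variables". On masking it says "Block size will be blinded from the primary investigator performing the study". It is silent about other staff, about who generates and holds the list, and about how an assignment is released. Under Initial Visit, "participants will be randomized to one of 3 intervention arms" after consent and assent, in the passive voice.

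Statistical Analysis gives the comparison of arms: "The change in %BMIp95 between week 24 and baseline was assessed using analysis of variance (ANOVA) for all participants via ITT", and then for the per-protocol and COVID-period sets. No site or stratum term is named. The same section goes on to mixed-effects models of %BMIp95 that adjust for recruitment site. As described, these relate change to participant characteristics and questionnaire scores; arm is not among the listed terms.

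**The concern.** A stratified design and its analysis should match. Stratification by a prognostic factor removes that factor's variation from the difference between arms. An analysis that ignores the factor still counts that variation as noise, so its standard error is too large for the design. Here a reader cannot tell whether strata existed or what they were, so cannot tell whether the ANOVA matches the design.

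Recruitment site is the natural candidate. The second Study Design section plans 202 youths at CHLA/AltaMed and 30 at each of three other sites. Clinic-arm care is centralised: "Those youth randomized to the in-clinic control arm will complete the intervention at CHLA or virtually via WebEx". Height and weight are measured at in-person visits and self-reported at virtual ones, so the way the outcome is obtained may vary with site. The plan already treats site as worth adjusting for elsewhere.

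The confounder statement is a separate, smaller fault. Permuted blocks fix the number per arm. Balance on a named covariate beyond what chance gives needs strata on that covariate, and the randomisation section lists none.

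**Working it through.** **The plan's own figure.** The point rests on no stated figure. The one figure attached to the three-arm %BMIp95 comparison is 89% power with 180 participants and effect size 0.29. Taking 0.29 as Cohen's f, one-way ANOVA power uses λ = N·f². N = 180 gives λ = 180 × 0.0841 = 15.14 and power 94.2%. N = 144 (180 less the 20% dropout in the power section) gives λ = 12.11 and power 87.9%, close to 89%. The figure therefore reproduces only after dropout. No site term enters either calculation.

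**Inputs.** Youths by site: 202 + 30 + 30 + 30 = 292. Three arms, two-sided alpha 0.05. *Assumed, because the documents do not give them:* the share s of outcome variance between sites (2% to 20%), and a block size of 6 in the simulations.

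**Case A: stratified by site, site left out of the ANOVA.** With blocks filled within each site, site variation cancels from the arm differences. Under no effect the between-arm mean square has expectation about (1 − s)σ², while the residual mean square stays near σ². The statistic behaves like (1 − s) × F(2, N − 3), so

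true type I error ≈ P[F(2, N − 3) > c / (1 − s)],

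with c = 3.027 for N = 292. The standard error is too large by a factor 1/√(1 − s).

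| s | c/(1 − s) | type I, formula | type I, simulated (20,000 trials) | SE factor |
|---|---|---|---|---|
| 2% | 3.089 | 4.7% | 4.6% | 1.01 |
| 5% | 3.186 | 4.3% | 4.2% | 1.03 |
| 10% | 3.363 | 3.6% | 3.7% | 1.05 |
| 20% | 3.784 | 2.4% | 2.4% | 1.12 |

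With N = 180 (c = 3.047) the formula gives 4.7%, 4.3%, 3.6% and 2.4%, so the choice between the two planned sample sizes does not matter here.

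**Case B: not stratified.** Simulated type I error without site is 5.3%, 5.1%, 4.9% and 5.0% for the same shares. The test is valid.

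**Power from adding site** (N = 292, illustrative f = 0.20, s = 10%). Site has four levels and uses 3 degrees of freedom, so the error degrees of freedom fall from 289 to 286.

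- With site in the model, λ rises from 292 × 0.04 = 11.68 to 11.68/0.9 = 12.98, and power is 90.4% by formula.
- Case A: 87.9% without site by formula; simulation gives 88% rising to 90%.
- Case B: simulation gives 86% rising to 89%.

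The gain is about 2 to 3 points in either case.

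**The case against.** Stratified block randomisation is a form of blocked randomisation, so the randomisation section may be incomplete rather than in conflict with Enrollment and Retention, and its aim of balancing confounders is what strata are for. This stands: the passages need completing and aligning, and they are not proof of two different schemes. It does not rescue the confounder sentence, which credits blocking and names no stratum.

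An unadjusted ANOVA is also a legitimate analysis. Without strata, chance imbalance does not bias it. For scale, take a gap of 8 between two arms at one small site, about 97 per arm (292/3), and an assumed 0.5 SD difference for that site. The contrast then shifts by 8/97 × 0.5 = 0.04 SD, against a standard error of √(2/97) = 0.14 SD. This stands too.

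A reader might infer something stronger: that site balance and allocation concealment were lost. The documents do not support it.

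- Site is never named as a stratum, so site balance is not a promise that was broken.
- Masking of block size is stated for the principal investigator. That it was hidden from nobody else is an inference from silence, and masking block size is not the same as concealing the next assignment.
- The alarming figures need different designs. One unstratified central list (blocks of 6) leaves a gap of 6 or more in at least one 30-youth site in about 77% of simulated trials. Certain prediction of 33% (blocks of 3) or 20% (blocks of 6) of assignments needs staff who know the block size and see every assignment in the block. If staff on a central list see only their own site's assignments, and even know block size and position, the share at blocks of 6 falls to 4.4% at CHLA and about 0.001% at a small site. Prediction returns in full only with separate site lists, where the imbalance disappears (gap 0 with blocks of 6).

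The concern about travel to CHLA is softened by the WebEx option, and by the free rides and parking validation in Enrollment and Retention.

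**Conclusion.** The point holds as a matter of efficiency and correct error bars. The week-24 comparison of arms omits a factor that is recorded and used elsewhere, and the protocol does not let a reader establish what the stratification was. The cost is modest: a conservative test if site was a stratum, and a small loss of power whether or not it was. Both sizes depend on the assumed variance share. If site explains almost nothing, the effect is negligible; if another prognostic factor was the stratum, the same reasoning applies with that factor's share. Nothing here shows inflated type I error or a biased estimate.

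The sequence holder and concealment from enrolling staff are undescribed. In an open trial that is a reporting gap worth closing, but it is not evidence that allocation was predictable or steered.

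**What to change.** 1. In Statistical Analysis, add recruitment site (CHLA/AltaMed, UCLA, Harbor-UCLA, Cedars Sinai), and any other factor actually used to stratify, to the week-24 comparison of arms. Site costs 3 degrees of freedom and no new data. That section is written in the past tense; if results are already known, report the adjusted comparison beside the ANOVA as specified and say when it was added.
2. Make Enrollment and Retention and Randomization and Blinding state the same method, the one actually used, with its strata or an explicit statement that there were none.
3. Delete the statement that blocking balances confounders.
4. State who generated and held the sequence, how assignments were released, and from whom block size and upcoming assignments were hidden.

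The total cost is one model term and a few sentences. No change to conduct is needed if enrolment is complete.
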